The main aim of this proposal is aligned with the studies above. We propose to improve the FFR-CT accuracy using the new opportunities offered by 3D printing. Namely we will develop very accurate coronary models using 3D printing and use these phantoms to optimize the FFR-CT approach. Next we propose to use the optimized approach to perform a small clinical study at Gates Vascular Institute where we will correlate the FFR-CT results with angio FFR and patient follow-up.

Summary of Proposed Research

Coronary Computed Tomography Angiography (CCTA) contrast opacification gradients and FFR-CT estimation can aid in the severity estimation of significant atherosclerotic lesions. Following this trend, we recently developed a collaboration between Brigham and Women's Hospital (BWH) and Gates Vascular Institute (GVI). We 3D-printed patient specific coronary phantoms at (GVI) and scanned them with a Toshiba Aquilion scanner to test several aspects of the contrast opacification gradients using a method established at BWH. Our initial results showed strong correlation between the flow in the phantom and opacification gradients. We believe that this approach could be further developed to test and validate FFR-CT algorithms. Currently, FFR-CT algorithms can only be optimized using theoretical models and can only be validated in large multi-center clinical trials. This phantom approach would allow optimization of FFR-CT algorithms with a measured validation technique without the need for large clinical trials. Thus we believe that this study will result in a FFR-CT algorithm/method with a better predictability for arterial lesion severity than those existing on the market today. Our approach is to use the infrastructure at GVI to perform a detailed validation of the FFR-CT method using 3D printed patient specific phantoms. Each patient will have a 3D phantom printed, containing the culprit lesion and used in a benchtop flow analysis. Flow measurements will be compared with: CT-FFR for both patients and phantoms, angio lab FFR measurements and 30 days follow-up. This pilot clinical study will include ~50 patients over a year and half at GVI. We are confident that this approach performed via 3D-phantom testing will prove the validity of FFR-CT based measurements as well as develop a new standard for validating FFR-CT algorithms

Objectives

- To build 50 3D printed patient specific phantoms for benchtop testing to determine pressure gradient along diseased vasculature
- To perform a detailed validation of the FFR-CT method using 3D printed patient specific phantoms
- Optimization of FFR-CT algorithms with a better predictability for arterial lesion severity without the need for large clinical trials

Hypotheses

Flow simulations in 3D printed patient specific phantoms will correlate with CT derived fractional flow reserve calculations. To demonstrate the concept feasibility, we propose to use 3D printed cardiac models for software validation using clinical evaluation as a gold standard. The clinical cases will be used both as ground truth to demonstrate the accuracy of the phantom validation as well as a pilot single-center clinical evaluation to demonstrate similar results to previously published clinical trials for algorithms similar to those being tested.

Study Design/ Procedures

Patients will be consented after CCTA. First requirement is that the patient has at least one lesion with >50% stenosis or 30-50% if clinically driven. Second requirement is that the patient undergoes a cath lab intervention. If one of the above requirements is not satisfied the patient will be removed from the study. Viable candidates based on inclusion/exclusion criteria will undergo clinically indicated first generation 320-detector row CCTA (Aquilion ONE, Canon Medical Systems, Tustin, CA) with 0.5 mm slice thickness, automated tube current modulation, 100 kVp, and a reconstructed voxel size of 0.625x0.625x0.5 mm. Next, the patient will undergo catheter lab procedure as clinically warranted. The invasive FFR will be done on the culprit lesion(s) for clinical purposes. Invasive FFR (I-FFR) will be recorded via pressure wire at a distance of two lesion lengths past the distal end of the lesion. A FFR cutoff value of less than or equal to 0.8 was used to determine hemodynamic significance.

For each patient a 3D printed phantom will be made and tested. Segmentation will be performed in Vitrea, vascular mesh sculpting in Autodesk Meshmixer, and 3D printed in a Stratasys Eden 260V printer (Stratasys, Eden Prairie, MN) printer. Figure 1 shows the model development process. Each 3D printed patient-specific model will be connected to a flow loop using the CardioFlow 5000 MR programmable physiological pulsatile flow pump (Shelley Medical Imaging Technologies, Toronto, Ontario, Canada) and a Benchtop FFR will be obtained. This pump introduced a physiologic human cardiac waveform and provided also an ECG signal triggered at points within the cardiac waveform. The viscosity of blood (approximately 3.7 cP) will be mimicked using a glycerol water solution of 40% water and 60% glycerol and measured using a viscometer. Figure 2 shows the benchtop flow system.

Reconstructed CCTA images were imported into Vitrea segmentation software (Vital Images, Minnetonka, MN) using the research-based CT-FFR algorithm [26-28]. The software analyzes four data volumes acquired a 70-99% of the R-R interval and computes the FFR based on the changes in vessel diameter and computational fluid dynamics.

Figure 1: Model development process. (a) The cardiac mesh was exported as a stereolithographic file from Vitrea into Autodesk Meshmixer. (b) The daughter branches off of the 3 main coronary arteries were cut off from the mesh. (c) The aortic root was extended at both the outlet and inlet with 30 mm diameter for later connections (red arrows). Cylindrical meshes were appended (red circles) to the aortic root and each of the coronary arteries for later pressure sensor connections. (d) Each coronary artery was extended. (e) A plane cut was administered at the vessel outlets for parallel ends. (f) A 2 mm wall was generated while preserving the geometry of the arteries. (g) A support structure is positioned around the model and the Boolean union operation is administered.

Figure 2: Benchtop flow system. (a) A 3D printed patient-specific coronary model is connected to a flow loop using the Cardio Flow 5000 MR programmable physiological pulsatile flow pump (Shelley Medical Imaging Technologies, Toronto, Ontario, Canada). The flow loop consisted of two compliance chambers, at the aortic inlet (D1) and distal to the coronary arteries (D2) to control pressure oscillation and distal resistance. Aortic base pressure and distal flow rate were controlled by adjustable mechanical clamps (R1 and R2 respectively), and flow rate was recorded using an ultrasonic flow sensor (S). Flow direction is indicated by blue arrows. (b) Detailed side view of the 3D printed coronary model with pressure sensors connected to the aorta and the LAD. (c) Coronary waveform within the coronary flow pump software to determine the flow rate (mL/s) as a function of time in a single cardiac cycle. (d) 52 patient-specific 3D printed coronary models assembled and ready to go through flow testing.

Inclusion Criteria

- Scheduled for clinically mandated elective invasive coronary angiography (ICA) or clinically mandated CTA
- \circ >18 yrs of age

Exclusion Criteria

- Less than 30 years of age
- Atrial fibrillation
- Renal insufficiency (estimated glomerular filtration rate (GFR) <60 ml/min/1.73 m2)
- Active Bronchospasm prohibiting the use of beta blockers
- Morbid obesity (body mass index 40 kg/m2)
- o Contraindications to iodinated contrast
- Emergencies requiring immediate intervention or patients unable to consent
- Patients not showing coronary calcium during Calcium Scoring procedures

Sample Size

To determine the numbers of phantoms needed for this study we treated 3D printing as a new diagnostic tool for which we needed to assess the accuracy of detecting significant FFR values. We used the sample size calculation proposed by Flahault et. al. [23].

$$n = \frac{\left(z_{\alpha/2}\sqrt{\hat{V}(\hat{A})}\right)^2}{L^2}$$

Since this is a technical feasibility study, we wanted to estimate the ROC area to within ± 0.6 ; thus, L=0.12 and the confidence level was set at 0.92 which corresponds to $z_{\alpha/2}=1.75$. For the variance function we used the formulation indicated by Obuchhowski et al. [24] who proposed an estimate of the variance function for the Receiver Operator Characteristic based on an exponential distribution.

$$\hat{V}(\hat{A}) = (0.0099 \times e^{a^2/2}) \times [(5a^2 + 8) + (5a^2 + 8)/R]$$

R denotes the ratio of the number of patients without the condition to patients with the condition in the study sample. Using results from previous reports on CT-FFR [25], we set R=1.2. For an AUROC=0.8 the parameter may be set to 1.19 [24]. Thus the number of samples with FFR<=0.80 are approximatively 23 and the total number of subject given by N_total=n(1+R) is approximatively 52.

Study Flow Chart

Statistical Analysis

The absolute error as a percentage with 95% confidence intervals and Pearson correlation values will be calculated to assess the results obtained from the benchtop flow testing and the CT-FFR software and how they compared to the I-FFR reference standard. A ROC curve will also be generated to determine the area under the curve (AUC) for B-FFR and CT-FFR when compared to I-FFR. Statistical analysis for the development of the ROC curves and correlation analysis will be completed within NCSS Statistical Software (NCSS, v.12, LLC, Kaysville, Utah).

References

1. Brown, B.G., et al., Quantitative coronary arteriography: estimation of dimensions, hemodynamic resistance, and atheroma mass of coronary artery lesions using the arteriogram and digital computation. Circulation, 1977. 55(2): p. 329-337.

2. Qureshi, A.I., et al., Prevention and treatment of thromboembolic and ischemic complications associated with endovascular procedures: Part I— Pathophysiological and pharmacological features. Neurosurgery, 2000. 46(6): p. 1344-1359.

3. [name], K.K., et al., Diagnostic accuracy of 3D deep-learning-based fully automated estimation of patient-level minimum fractional flow reserve from coronary computed tomography angiography. European Heart Journal - Cardiovascular Imaging, 2019.

4. Tang, C.X., et al., Diagnostic performance of fractional flow reserve derived from coronary CT angiography for detection of lesion-specific ischemia: A multi-center study and meta-analysis. Eur J Radiol, 2019. 116: p. 90-97.

5. Morris, P.D., et al., Virtual fractional flow reserve from coronary angiography: modeling the significance of coronary lesions: results from the VIRTU-1 (VIRTUal Fractional Flow Reserve From Coronary Angiography) study. JACC Cardiovasc Interv, 2013. 6(2): p. 149-57.

6. Morris, P.D., et al., Computational fluid dynamics modelling in cardiovascular medicine. Heart, 2016. 102(1): p. 18-28.

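### The third objective, better-predicting FFR-CT through optimisation, has no described tuning step, no stated tuning set and no comparator, so the planned analysis cannot answer it

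*Combined protocol and SAP*

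**What the plan says.** The opening text, before the Summary of Proposed Research, sets out two steps. The first is to "use these phantoms to optimize the FFR-CT approach". The second follows: "Next we propose to use the optimized approach to perform a small clinical study at Gates Vascular Institute".

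The Summary of Proposed Research states the authors' belief that "this study will result in a FFR-CT algorithm/method with a better predictability for arterial lesion severity than those existing on the market today". It gives the size as "This pilot clinical study will include ~50 patients over a year and half at GVI" and has one phantom printed for each patient.

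The Objectives begin with "To build 50 3D printed patient specific phantoms for benchtop testing", continue with validation of FFR-CT using the phantoms, and end with "Optimization of FFR-CT algorithms with a better predictability for arterial lesion severity without the need for large clinical trials". The Hypotheses are more modest. They expect phantom flow to correlate with CT-FFR, and the pilot to give results comparable to those of earlier published trials of similar algorithms. They also give the clinical cases two roles: reference truth for the phantom validation, and the pilot clinical evaluation.

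Study Design/Procedures describes one research CT-FFR algorithm. Statistical Analysis plans percentage absolute error with 95% confidence intervals, Pearson correlation, and this: "A ROC curve will also be generated to determine the area under the curve (AUC) for B-FFR and CT-FFR when compared to I-FFR".

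**The concern.** A claim of better prediction is a claim about a difference, so something must stand on the other side of it. The methods name neither a version of CT-FFR from before optimisation nor a marketed product. A single AUC against I-FFR, however well estimated, cannot show that optimisation helped or that the method outperforms other software.

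The second issue is where the tuning happens. The methods and statistics sections name no parameter to be adjusted, no rule for choosing its value, no point at which the version is fixed and no set of phantoms for the purpose. The only phantoms assigned to FFR-CT work are those made from the study patients. If these are used for tuning and the same patients then supply the reported AUC, that AUC is partly a measure of fit. If no tuning takes place, there is no such bias, but the third objective is not addressed at all.

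**Working it through.** **1. What the sample size covers.** Inputs from Sample Size: z = 1.75, L = 0.12, a = 1.19 (AUC 0.80), R = 1.2. The formulas are n = z²V/L² and N = n(1 + R).

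- With a negative exponent and a second term of (a² + 8)/R: V = 0.0099 × e^(−0.708) × [15.08 + 9.416/1.2] = 0.1118. Then n = 3.0625 × 0.1118/0.0144 = 23.8 and N = 23.8 × 2.2 = 52.3. This reproduces the plan's 52.
- The variance formula as it appears in the text (positive exponent, 5a² + 8 in both terms) gives V = 0.556, n = 118.2 and N = 260. That may be a transcription matter, and nothing below depends on it.

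Either way, the calculation sets the precision of one AUC. It contains no difference between two algorithms.

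**2. Objectives set against analyses.**

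| Aim | Needed to answer it | Planned |
|---|---|---|
| Build and test phantoms | Benchtop measurements | Yes |
| Validate FFR-CT with phantoms | B-FFR and CT-FFR against I-FFR | Yes |
| Optimise FFR-CT for better prediction | Starting against optimised version, same patients | No |
| Predict better than marketed tools (a belief) | A marketed tool on the same patients | No |

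**3. Optimism if tuning uses the study patients.** This is a simulation with assumed inputs: 24 patients with and 28 without significant FFR (52/2.2 = 23.6, rounded to 24), and k candidate settings, each with true AUC 0.80 (separation 1.19) and within-patient correlation ρ between settings. One setting is kept and its AUC is read on the same 52 patients.

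| k | Best AUC against I-FFR kept: ρ = 0.9 | ρ = 0.7 |
|---|---|---|
| 5 | 0.823 | 0.843 |
| 10 | 0.831 | 0.855 |
| 20 | 0.840 | 0.864 |

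Subtracting 0.80 gives a false gain of about 0.02 to 0.06.

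If the setting kept is instead the one that correlates best with B-FFR, the apparent AUC over the same k and ρ is 0.803 to 0.827, a gain of about 0.00 to 0.03. Here B-FFR also has separation 1.19, and its loading on the shared patient error is taken as 0, 0.5 or 0.8. Against L = 0.12, the largest gains are a quarter (0.03/0.12) and a half (0.06/0.12).

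**4. What a before-and-after comparison could show in 52 patients.** Hanley-McNeil standard errors with 24 and 28 patients are 0.0633 for AUC 0.80 and 0.0558 for AUC 0.85. For a paired difference, SE² = 0.0633² + 0.0558² − 2r(0.0633)(0.0558), and power is approximately Φ(0.05/SE − 1.96). The correlation r is assumed.

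| r | SE of difference | Power for 0.80 against 0.85 |
|---|---|---|
| 0.3 | 0.0707 | 0.105 |
| 0.5 | 0.0599 | 0.13 |
| 0.7 | 0.0466 | 0.187 |
| 0.8 | 0.0383 | 0.256 |
| 0.9 | 0.0276 | 0.44 |

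So the paired AUC difference is worth reporting as an estimate, but it would be a weak test.

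**The case against.** The study calls itself a pilot and a technical feasibility study, and its stated hypotheses concern correlation and agreement with published results. Those can be answered as planned. This stands, and it confines the point to the third objective and the market sentence.

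A reader might infer that the same patients are certain to supply both tuning and testing. The documents do not say so. They place optimisation before the clinical study, mention patient-specific phantoms already printed and scanned at the site, and give the 50 study phantoms a stated purpose of benchtop testing. The earlier phantoms are described only in connection with contrast opacification gradients and are not assigned to FFR-CT tuning. One phantom per patient and the dual role of the cases make overlap likely, but it remains an inference. The copy reviewed also lacks an early portion and the flow chart. If either names a tuning set, the overlap falls away, but the missing comparator in the statistical section remains.

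A reader might also take the 0.02 to 0.06 inflation as the expected size. That requires settings to be picked on I-FFR. The plan speaks of optimising on phantoms, which is closer to picking on B-FFR, where the gain is about 0.00 to 0.03.

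Finally, a reader might infer that the plan promises a superiority test against marketed software. It does not: that sentence is worded as a belief, and the Hypotheses aim only for comparable results. But the two statements do not fit together, and the third objective, which is a formal aim, still claims better predictability.

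**Conclusion.** The point holds in a limited form. Followed exactly, the plan leaves the third objective and the expectation about marketed algorithms unanswerable, because one CT-FFR algorithm is compared only with I-FFR. This conclusion comes from the text and needs no numerical assumption. The first two objectives are unaffected.

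Optimism in the CT-FFR AUC is conditional on tuning with the study phantoms. Its size then rests on the assumed number of settings, their correlation and the tuning target. At most it is moderate beside the planned precision, and it may be negligible. The change should be made, but it does not threaten the validation part of the study.

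**What to change.** 1. Run CT-FFR on each CCTA already held, once with the starting settings and once with the optimised settings. Report the paired difference against I-FFR in absolute error (main) and in AUC, as estimates with confidence intervals. State that 52 patients give low power for an AUC gain of 0.05, about 10% to 44% under the assumed correlations.
2. State which phantoms are used for tuning. If they are the study phantoms, choose settings on B-FFR without using I-FFR, and score each patient with settings tuned without that patient, for example by 5- or 10-fold cross-validation. If they are earlier phantoms, say so; cross-validation is then unnecessary.
3. Remove the comparison with marketed algorithms from the Summary of Proposed Research ("better predictability for arterial lesion severity than those existing on the market today"), or limit the claim to improvement over the starting version of the tested algorithm. This also brings it into line with the Hypotheses.
4. If no optimisation will be done, drop the third objective.

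The cost is a second software run on existing images, some extra analysis and a less favourable claim. Fold-wise tuning means repeating the optimisation once per fold, and it presumes that the research software has settings that can be adjusted, which the documents do not show. No patients or patient procedures are added.

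### The aim of showing results similar to published trials has no reference AUC, margin or planned AUC interval, and about 52 patients cannot support that conclusion

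*Combined protocol and SAP*

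**What the plan says.** In the combined protocol and SAP, the Hypotheses section gives the clinical cases two uses: as ground truth for the phantom work, and as a single-centre pilot "to demonstrate similar results to previously published clinical trials for algorithms similar to those being tested". No trial is named as the benchmark. References 26-28 are cited under Study Design/ Procedures as the source of the CT-FFR algorithm, without accuracy figures.

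The Summary of Proposed Research states the belief that the study "will result in a FFR-CT algorithm/method with a better predictability for arterial lesion severity than those existing on the market today".

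The Sample Size section is built on AUC precision: "we wanted to estimate the ROC area to within ± 0.6 ; thus, L=0.12", and "the confidence level was set at 0.92 which corresponds to" z = 1.75. With a planning AUC of 0.8 and R = 1.2 it arrives at about 23 patients at or below the FFR cutoff and about 52 in all.

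The Statistical Analysis section attaches 95% intervals to the percent absolute error and lists Pearson correlations. For discrimination it says only: "A ROC curve will also be generated to determine the area under the curve (AUC) for B-FFR and CT-FFR when compared to I-FFR". It states no interval, test, benchmark or decision rule for the AUC.

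**The concern.** A similarity claim needs a value to be similar to, a difference small enough to ignore, and an estimate precise enough to exclude larger differences. The plan supplies none of these in its analysis. Without them, similar is likely to mean not visibly different, and a study of this size will often fail to show a difference that matters. The rule could also be settled after the data are seen.

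The analysis section also does not commit to reporting the one quantity the study was sized for, the uncertainty of the AUC. A reader given only point AUCs could take closeness to a published figure as confirmation when the data are compatible with clearly worse performance.

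**Working it through.** **Inputs from the documents.** z = 1.75, L = 0.12, a = 1.19, R = 1.2, planning AUC 0.8, about 23 patients at or below the cutoff, N about 52, so 52 − 23 = 29 above it.

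**The plan's own figure.** n = z²V/L² and N = n(1 + R).

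- Variance as printed: V = 0.0099 × e^(a²/2) × [(5a² + 8) + (5a² + 8)/R] = 0.556, so n = 3.0625 × 0.556/0.0144 = 118 and N = 260. This does not give 52.
- With a negative exponent and (a² + 8)/R as the last term: V = 0.1118, n = 23.8, N = 52.3. This does give 52.

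The stated sample size is therefore consistent with a formula close to the printed one. That discrepancy, and the printed ± 0.6 beside L = 0.12, are separate text corrections. What follows uses only the resulting 23/29 split.

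**Precision of the AUC.** The Hanley-McNeil variance is [A(1 − A) + (n₁ − 1)(P₁ − A²) + (n₀ − 1)(P₂ − A²)]/(n₁n₀), with P₁ = A/(2 − A) and P₂ = 2A²/(1 + A). At A = 0.80, n₁ = 23, n₀ = 29:

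[0.16 + 22 × 0.0267 + 28 × 0.0711]/667 = 0.0041, so SE = 0.064 and the 95% half-width is 1.96 × 0.064 = 0.126.

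The average DeLong half-width in simulation is 0.121.

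**Chance that a truly worse algorithm passes.** The documents define no rule, so one is assumed: the confidence interval includes the published AUC, which is treated as fixed. The true AUC is set 0.10 lower. Scores are binormal with equal variance, one value per patient, 23/29 split, 20,000 replicates per row, DeLong standard errors.

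| Published / true AUC | 95% CI, untransformed | 95% CI, logit | 92% CI, untransformed | 92% CI, logit |
|---|---|---|---|---|
| 0.80 / 0.70 | 78% | 67% | 69% | 60% |
| 0.85 / 0.75 | 75% | 60% | 66% | 53% |
| 0.90 / 0.80 | 71% | 48% | 60% | 41% |

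A 24/28 split gives almost the same results. If similar instead means a point estimate within 0.10 of the published value, the pass rate is about 52%.

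**Power if a margin were set.** Assume a margin of 0.10 below a fixed reference, one-sided 2.5%, and a true AUC equal to the reference. Power = Φ(0.10/SE − 1.96). At 23/29 the SE is 0.064, 0.057 and 0.047 for references 0.80, 0.85 and 0.90, which gives power of about 34%, 42% and 57%. For 80% power the total N would be about 163, 127 and 87.

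**Choice of interval.** At true AUCs of 0.80, 0.85 and 0.90 the untransformed DeLong 95% interval covers about 93%, 92% and 90% to 91%. The logit-scale interval covers about 95% to 96%.

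**Pearson r.** The Fisher-z standard error at N = 52 is 1/√49 = 0.143. An observed r of 0.70 would have a 95% interval of 0.53 to 0.82.

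**The case against.** The strongest reply is that this is a pilot and technical feasibility study, sized for estimation. The Sample Size section does set an AUC precision target, so the plan does not ignore AUC uncertainty. ROC software may also print an interval whether or not the text asks for one. The first part stands: the gap lies in the analysis section, not in the design. But pilot status supports estimating the AUC. It does not support demonstrating similarity, and a design built on precision is a reason to commit to reporting it.

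It is also fair that the pass rates are not properties of the plan. They depend on a rule and a reference that the documents do not contain, and other rules give lower figures.

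Some stronger readings are tempting, and the documents do not support them:

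- *A worse algorithm would nearly always look similar.* The calculated rates run from 41% to 78%, so often is the right word.
- *The plan makes a superiority claim.* The sentence on marketed products is introduced as a belief in a summary, and no test of it is planned.
- *Nothing is compared in the same patients.* B-FFR and CT-FFR are both assessed against I-FFR in the same patients.
- *CCTA percent stenosis should be added as a benchmark because it is already in hand.* The documents give stenosis only as an eligibility band: "First requirement is that the patient has at least one lesion with >50% stenosis or 30-50% if clinically driven". They do not say that a percent value is kept as study data. Selection on stenosis would restrict its range and tend to depress its AUC, and added value over stenosis is not a stated aim.

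**Conclusion.** The concern holds in a limited form. The similarity aim has no reference AUC, named comparator or margin, and the analysis section plans no interval for the AUC on which the study was sized.

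Under the assumed inclusion rule with 95% intervals and published AUCs of 0.80 to 0.90, a 0.10 shortfall would pass about 48% to 78% of the time. At the plan's own 92% level the range is about 41% to 70%. These figures rest on a binormal model, one value per patient, a 23/29 split and a published AUC without sampling error. No single figure should be quoted without those conditions.

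That reasonable rules give such different answers is part of the point, since the plan fixes none of them. Adding a 0.10 margin now would not rescue the aim, because power would be only about 34% to 57%. The study can estimate the AUC; as planned it cannot demonstrate similarity.

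**What to change.** 1. In Statistical Analysis, report the AUCs of B-FFR and CT-FFR against I-FFR with 95% confidence intervals, by DeLong on the logit scale or by a bootstrap that resamples patients. Avoid the untransformed DeLong interval because it under-covers at this sample size. Report Pearson r with a Fisher-z 95% interval.
2. In Hypotheses, replace the similarity aim with wording such as: *to estimate the AUC with its 95% confidence interval and set it beside named published values*. Name those studies and values before the analysis.
3. State that no similarity or better-than-market conclusion will be drawn from this pilot, and qualify the sentence in the Summary of Proposed Research to match.

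The cost is a few lines of text and routine analysis of data already planned, with no extra patients or procedures. The downside is a weaker headline claim. If the sponsor wants to keep a similarity claim, it needs a stated reference and margin and a larger study, on the order of 87 to 163 patients under the assumptions above.

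### Does the undefined cath lab entry requirement put the reference standard or the planned case mix at risk?

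*Combined protocol and SAP*

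**What the plan says.** Study Design/ Procedures first requires a lesion of a given degree of stenosis, then adds: "Second requirement is that the patient undergoes a cath lab intervention". The consequence of failing either condition is stated: "If one of the above requirements is not satisfied the patient will be removed from the study". Later in the same paragraph the step has a different name: "Next, the patient will undergo catheter lab procedure as clinically warranted". The reference measurement follows: "The invasive FFR will be done on the culprit lesion(s) for clinical purposes". It is to be recorded by pressure wire at a set distance beyond the lesion, and 0.8 or below counts as haemodynamically significant.

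Three other places bear on the point:

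- Inclusion Criteria admits patients by either of two routes: "Scheduled for clinically mandated elective invasive coronary angiography (ICA) or clinically mandated CTA".
- Sample Size sets R=1.2 and explains it: "R denotes the ratio of the number of patients without the condition to patients with the condition in the study sample".
- Statistical Analysis assesses benchtop FFR and CT-FFR by error, Pearson correlation and ROC area, and by "how they compared to the I-FFR reference standard".

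**The concern.** *Intervention* can mean treatment of the lesion or simply a visit to the catheter laboratory. The exclusion criterion "Emergencies requiring immediate intervention or patients unable to consent" appears to use it in the first sense. If the entry rule meant that too, a patient whose I-FFR was above 0.80 and who was left untreated would be removed, although that patient is a valid negative for the ROC curve. The sample would then hold fewer negatives than R=1.2 assumes. If those kept lay mostly near the cutoff, AUC and correlation would fall for reasons unrelated to either method's accuracy.

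The second sense leaves a different gap. Patients may enter through a CT angiogram alone, the catheter procedure depends on clinical need, and I-FFR is taken for clinical purposes. A catheterised patient with no pressure-wire value would meet both written conditions and still be useless for the analysis. The plan gives no rule for that case and no allowance for it in the 52.

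**Working it through.** **The plan's own figure.** Inputs from Sample Size: z=1.75, L=0.12 (it enters the formula as a half-width), a=1.19, R=1.2; n = z²V/L² and N = n(1+R).

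- Variance as printed: V = 0.0099·exp(a²/2)·[(5a²+8)+(5a²+8)/R] = 0.556, so n = 118.2 and N = 260. This does not give 52.
- With a negative exponent and (a²+8)/R as the last term: V = 0.0099 × 0.4926 × (15.08 + 7.85) = 0.112, n = 3.0625 × 0.1118/0.0144 = 23.8, N = 23.8 × 2.2 = 52.3. This reproduces the stated 52, so I use it below. The printed formula is a separate matter.

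At N=52 and R=1.2 there are 52/2.2 = 23.6 patients at or below 0.80 and 28.4 above.

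**Which reading the text supports.** For catheterisation: the later sentence in the same paragraph calls the step a procedure; I-FFR on the culprit lesion follows it; a cutoff is then applied, which presupposes patients on both sides; and R=1.2 expects more patients above 0.80 than below. For treatment: one phrase in an exclusion criterion about emergencies, which defines nothing. R=1.2 is therefore better taken as evidence against the treatment reading than as a conflict with it.

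**Size under the treatment reading.** Let q be the share of patients above 0.80 who are removed. The documents give no q. R becomes 1.2(1−q).

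| q | R | N needed for L=0.12 | L if refilled to 52 | L if not replaced |
|---|---|---|---|---|
| 0 | 1.2 | 52 | 0.120 | 0.120 |
| 0.25 | 0.9 | 50 | 0.118 | 0.127 |
| 0.50 | 0.6 | 51 | 0.119 | 0.140 |
| 0.75 | 0.3 | 63 | 0.132 | 0.171 |

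If recruitment refills to 52, precision is no worse than planned even with half the negatives removed.

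Bias needs selective loss. I simulated it with I-FFR normal, SD 0.10, 1/2.2 = 45% at or below 0.80, and method error set so that the full-sample AUC is 0.80. Losing half the negatives at random leaves AUC at 0.80 and moves r from 0.64 to 0.63. Keeping only negatives between 0.80 and 0.90 gives AUC 0.75 (0.74 to 0.77 for SD 0.12 to 0.08) and r 0.54. Keeping only 0.80 to 0.85 gives AUC 0.71 and r 0.49. Nothing in the documents suggests retention of that kind.

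**Size under the catheterisation reading.** If a share m of the 52 has no I-FFR, at random, L = 1.75·√(V/n) with n = 23.6(1−m). For m = 0, 10%, 20% and 30% this gives 0.120, 0.127, 0.135 and 0.144. To finish with 52 evaluable patients, enrolment would have to be 52/(1−m), or 58, 65 or 75. The values of m are assumptions. The Hanley–McNeil variance gives a lower series (0.111, 0.118, 0.125, 0.134 at the 92% level), but L=0.12 was set against the plan's own variance function, so the first series is the right one to compare with it.

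**What a rewritten rule would do.** Suppose staying in required a recorded I-FFR. The analysed patients would be those with I-FFR. Under the present text, read as catheterisation, they are also those with I-FFR, because error, correlation and ROC area cannot be computed without it. The two analysis sets are the same.

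**The case for a change.** The best argument for a change is that the criterion selects on the wrong event under either reading. As treatment it discards valid negatives; as catheterisation it does not secure the reference value. One sentence tying entry to a recorded I-FFR, whether or not treatment followed, would settle both at almost no cost and touch nobody's care. In the variance form that reproduces 52 there is no slack, so any missing I-FFR misses the target half-width. Removals and the achieved ratio could also be reported.

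Some of this stands. The term is undefined, a recorded I-FFR is not a written condition, and 52 carries no margin. The rest does not lead to a change. The harmful reading is the less likely one, and its bias also needs patients above 0.80 to go mostly untreated and those kept to cluster near the cutoff. I-FFR is planned outright for the culprit lesion, and the Summary of Proposed Research likewise compares flow measurements with angio lab FFR, so it is not left to chance. A wording change would not restore missing values; only more enrolment would, which is a resource decision for a feasibility pilot. R=1.2 is a planning input and not a recruitment quota, and the achieved ratio is plain from the data. The plan cannot be faulted for omitting a report of removals, because the study flow chart is not shown in the text available. The study is single-centre, so the rule will not be read differently from site to site.

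**Conclusion.** No change follows. The paragraph uses two names for one step and leaves unwritten a rule that the analysis imposes anyway. Read in context, the condition is that the patient is catheterised; I-FFR is then planned, and a patient without it drops out of an I-FFR comparison whatever the protocol says.

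The remaining cost is precision: roughly 0.007 on the half-width if 10% lack I-FFR and 0.024 if 30% do, assuming values are missing at random and the variance form that yields 52. The treatment reading would lower R by an amount the documents do not give, with little effect on precision up to half the negatives lost if recruitment refills to 52. This conclusion rests on the catheterisation reading. If the trial team in fact removed patients because they were not treated, the negatives would be incomplete and the AUC would have to be interpreted in that light.
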